8.3. To monitor rifampicin resistance among leprosy patients

All leprosy patients with a positive/negative test result for Rifampicin resistance will be included in a random effects logistic regression model with rifampicin resistance (0/1) as dependent variable, island as explanatory variable, and with 'block' (as described above, eight on Anjouan, four on Mohéli, four to six on Madagascar) and 'village' as nested random effects. Based on this model, prevalence of Rifampicin resistance per island will be estimated with 95% confidence interval.

9. Safety analyses

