2.1. Study design

The PEOPLE study is a cluster randomized trial. There will be four door-to-door surveys of which the first one will allow us to calculate a baseline leprosy prevalence

per island. On the Comoros villages have been randomized after having been grouped by island into 'Blocks' of four in decreasing order of incidence over the period 2013-2017. Within each block villages were randomly and mutually exclusively allocated to the four study arms. For the study district in Madagascar reliable incidence estimates were not available. For that reason randomization for Madagascar is foreseen only for the end of the first study year, once the first screening round has been completed.

There will be four study arms to which villages on Madagascar and the Comoros islands Anjouan and Mohéli will be randomly allocated. These villages have been preselected based on reported leprosy incidence over the period 2013-2017. In all four study arms, annual door-to-door surveys will be conducted covering entire villages. All permanent residents will be invited for screening for leprosy. Leprosy patients (further referred to as 'index patients') detected will be offered free treatment according to the international and country guidelines. Depending on the study arm, contacts of leprosy patients will be offered PEP. In arm 1 no PEP will be provided, which is the current routine care on Madagascar and the Comoros. In arms 2, 3 and 4 a single dose of 20 mg per kg bodyweight of Rifampicin (hereafter called 'SDDR-PEP') will be offered to all eligible participants who have not received Rifampicin in the preceding 2-year period. In arm 2 only household contacts of an index patient will be provided with SDDR-PEP, which target group is considered the standard approach when PEP is provided for leprosy. In arms 3 and 4 SDDR-PEP will also be provided to neighbourhood contacts living within a radius of 100 meter of an index patient. In arm 3 all such contacts (including household contacts) will be provided SDDR-PEP, in arm 4 SDDR-PEP will be provided to all household contacts and to all those within the 100-meter perimeter testing positive to a serological screening test. If in arms 3 or 4 more than 50% (arm 3) or 75% (arm 4) of the population live within 100 meters of an index case, the entire village will in principle be eligible for PEP.

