2.2. Study objectives

Primary objective:

To compare effectiveness in curbing transmission of leprosy of three different approaches of post exposure prophylaxis

Secondary objectives:

1. To assess cost and feasibility of SDDR-PEP under program conditions
2. To identify patterns of clustering in transmission of leprosy, allowing better targeting of control measures
3. To monitor rifampicin resistance among leprosy patients
4. To estimate incidence and prevalence of smear positive pulmonary tuberculosis in the study villages

3. Deviations from protocol

In the protocol one of the secondary objectives was to estimate incidence and prevalence of smear positive pulmonary tuberculosis (see section above). The criterion to collect sputum was reported cough of 2 weeks duration or more. On a total population screened of just over 102,000 during the first year, only 115 (0.11%) reported such

cough. Either the question is not properly understood or cough is not a good screening criterion in the context of this study population. It was therefore decided to drop this secondary objective.

4. Description of study population

The study population will be described overall, and in each island (Anjouan, Mohéli, Madagascar) separately.

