5.1. Patient populations

Note that in Madagascar enrolment/randomization will only take place at the second survey. Hence for Madagascar only data from the second survey onwards will be used for the primary objective. For secondary objectives 2 and 3 data from the first survey will also be used.

We will analyse the efficacy data using Intention-to-Treat and Per-Protocol approaches, with Intention-to-Treat as primary approach.

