Mixed effects Poisson model (same model as for the main analysis) with study arm (only when comparing 2019 to 2020 data) and distance to nearest index case as fixed covariates will be used to test for an association between distance to index case and leprosy incidence rate. We will compare six distance categories: same household, neighbors at < 25 meters and neighborhood contacts at 25-<50 meters, at 50 - < 75 meters, at 75 - < 100 meters and at 100 meters or beyond. Two models will be fitted. The first model will use leprosy diagnosis at the time of the survey in 2019 (either a new diagnosis or a patient still on treatment) as outcome and distance to nearest index case from 2019 as independent variable, the second model will use incident leprosy cases in 2020 as outcome and distance to nearest index case from 2019 as independent variable. In addition we will use Kulldorff's spatial scan statistic to fit a purely spatial Poisson model to identify clusters of high leprosy prevalence.

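### The resistance analysis in SAP section 8.3 yields one pooled prevalence per island, so it cannot show change during the trial or a difference between PEP and no-PEP villages

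*SAP*

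**What the plan says.** Secondary objective 3 (SAP section 2.2) is "To monitor rifampicin resistance among leprosy patients". Section 5.2 says resistance is determined by molecular markers.

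Section 8.3 gives the whole analysis. On who enters: "All leprosy patients with a positive/negative test result for Rifampicin resistance will be included in a random effects logistic regression model". On the fixed part: "with rifampicin resistance (0/1) as dependent variable, island as explanatory variable". On the random part and the output: "and 'village' as nested random effects. Based on this model, prevalence of Rifampicin resistance per island will be estimated with 95% confidence interval". Block is the other random effect. No table or term for survey, period, arm or earlier SDDR-PEP is planned.

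Three other statements bear on who is combined:

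- Section 2.1: "There will be four door-to-door surveys".
- Section 2.1: "In arm 1 no PEP will be provided, which is the current routine care on Madagascar and the Comoros". Arms 2, 3 and 4 are offered single-dose rifampicin.
- Section 5.1, in a paragraph about Madagascar: "For secondary objectives 2 and 3 data from the first survey will also be used". For the Comoros, inclusion of first-survey patients follows from the unrestricted wording of section 8.3.

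**The concern.** The trial offers rifampicin to contacts in three of four arms and sets itself the objective of monitoring rifampicin resistance among patients. A reader will expect to learn at least whether resistance among later cases resembles that at baseline, and whether it looks alike with and without PEP. The planned output answers neither question. It averages over time and over arms, including a randomised no-PEP arm that would be the natural comparator.

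No other part of the SAP fills the gap. The safety analysis (sections 9.1 and 9.2.1) covers only people who took a dose, and only events up to three days afterwards. Section 8.2 does bring arm and calendar year into its distance models ("with study arm (only when comparing 2019 to 2020 data) and distance to nearest index case as fixed covariates"), so such terms are within the plan's own practice.

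**Working it through.** The SAP states no sample size, expected prevalence or power for this objective, so there is no figure to reproduce. The check is structural, followed by illustrations on assumed counts.

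**1. What the model can see.** The only inputs are the 0/1 result, island, block and village. The likelihood therefore depends on the data only through the resistant and tested totals in each village.

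- Moving resistant cases between surveys within a village leaves every estimate unchanged.
- Arm is constant within a village but is not in the model. A real arm difference would go into between-village variance without a label.

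**2. Time, illustrated.** Assume one island, four surveys, 100 tested per survey and 12 resistant in all. The fixed part of the planned model is then an intercept.

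- Prevalence = 12/400 = 3.0%.
- Logit = ln(12/388) = −3.476; SE = √(1/12 + 1/388) = 0.293.
- 95% limits on the logit scale: −3.476 ± 1.96 × 0.293, which back-transform to 1.7% and 5.2%.

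| Resistant per survey | Planned output | OR per survey if survey is added (95% CI) |
|---|---|---|
| 3, 3, 3, 3 | 3.0% (1.7 to 5.2) | 1.00 (0.60 to 1.67) |
| 0, 1, 4, 7 | 3.0% (1.7 to 5.2) | 2.85 (1.36 to 5.97) |
| 7, 4, 1, 0 | 3.0% (1.7 to 5.2) | 0.35 (0.17 to 0.74) |

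These fits leave out the random effects. By step 1, including them would not let the model see time.

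**3. Arm, illustrated.** With 100 tested per arm, 3, 3, 3, 3 resistant in arms 1 to 4 and 0, 4, 4, 4 resistant both give 12/400 = 3.0%. The first pattern has 3% everywhere. The second has 0% in arm 1 and 12/300 = 4% in arms 2 to 4.

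**4. Averaging over period.** If a share w of tested patients is from baseline, the pooled value is w·p0 + (1 − w)·p1.

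- w = 0.5, 1% then 5%: 0.5 × 1 + 0.5 × 5 = 3.0%.
- w = 0.5, 0% then 3%: 0.5 × 0 + 0.5 × 3 = 1.5%.
- w = 0.6, 1% then 5%: 0.6 × 1 + 0.4 × 5 = 2.6%.

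All inputs are assumed. The lines show the mechanism, not an expected result.

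**5. Could a contrast be estimated?** Power to compare two periods, two-sided 0.05, before any allowance for clustering:

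| Tested per period | 1% v 3% | 1% v 5% |
|---|---|---|
| 100 | 0.17 | 0.38 |
| 200 | 0.30 | 0.65 |
| 400 | 0.52 | 0.91 |
| 800 | 0.82 | over 0.99 |

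For 80% power about 769 per period (1% v 3%) or 285 per period (1% v 5%) would be needed. A formal test may therefore be out of reach, while a table is always possible.

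**6. Where to cut time.** Section 5.1 places enrolment and randomisation in Madagascar at the second survey. Cases found there at that survey precede any effect of trial PEP. Splitting first survey from later surveys on every island would count them as post-PEP. The cut has to be the enrolment survey: the first on the Comoros, the second in Madagascar.

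**The case against.** The best defence is that section 8.3 delivers what it promises. The SAP does not define monitoring, objective 3 mentions neither time nor arm, and the stated output is prevalence per island, for which the model is adequate. Objectives are taken from a protocol that is not to hand, and section 1 leaves room for additional analyses. This stands in part: the section contradicts nothing else in the SAP, and reading the objective as tracking change is an interpretation, though the natural one. An option to do more is not a commitment to do it.

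A reader might go further and infer that the plan would hide a rise in resistance, and that this is the chief population-level danger of PEP. The SAP does not support that. It nowhere says that resistance is expected to rise or ranks it among the risks, and it gives no numbers from which masking could be sized.

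It is also fair to object that comparing later cases by whether they took SDDR-PEP is not a randomised comparison. Under section 2.1, receipt depends on household or nearness to an index patient and, in arm 4, on serology for neighbours. That objection stands in full and shapes the remedy. So does the objection that resistance may be too rare to model.

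**Conclusion.** The point holds as a limit on what section 8.3 can report. With island as the only fixed effect and one prevalence per island as the only output, neither change over the trial nor a difference between PEP and no-PEP villages can be seen. This follows from the model's form and needs no assumption about resistance rates. How much is lost in practice cannot be stated, since it depends on the number tested, the share found at baseline and the true prevalence, none of which the SAP gives. The matter concerns a secondary objective, and the primary efficacy analysis is untouched.

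**What to change.** Keep the per-island estimate and add to section 8.3:

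- A table of resistant/tested with exact 95% intervals, by island and period. Baseline is every case found up to and including the enrolment survey (first survey on the Comoros; first and second in Madagascar). The later period is every case found after it.
- Within the later period, a split by randomised arm: arm 1 against arms 2 to 4.
- Period and arm terms in the logistic model only if the number of resistant isolates allows, with that condition written down in advance.
- Any split by individual SDDR-PEP receipt labelled descriptive only, because receipt is selected.
- A sentence saying that absence of a detected rise is not evidence of no rise.

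The cost is a few lines of SAP text and one table from results the plan already uses. The drawback is small cells with wide intervals. Exact binomial intervals also ignore clustering within villages, so they may be somewhat too narrow if resistant isolates cluster; a footnote should say so.

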9.1. Safety analysis population

For the analysis of safety outcomes, all participants who effectively received a SDDR-PEP dose are included in the safety analysis (all-patients-treated approach).

9.2. Safety outcomes and analyses

9.2.1. Adverse events

General aspects: Adverse events (AEs) will be coded using the Medical Dictionary for Regulatory Activities (MEDDRA) and will be reported based on MEDDRA preferred terms and body systems. All AEs will be analyzed based on counts of participants with a specific category and not on counts of individual adverse events. The relationship between AEs and treatment is determined by the local investigator and categorized as "drug-related" if possibly, probably or definitely related to treatment. Only adverse events that occur between the administration of the drug and three days after administration will be recorded for study purposes.

The following summaries will be presented:

- a. description of all deaths of participants up to three days after SDDR-PEP administration;
- b. the total number and percentage of participants with any AE by preferred term and body system up to three days after SDDR-PEP administration;
- c. the total number of participants and percentage with any drug-related AE by preferred term and body system up to three days after SDDR-PEP administration;
- d. the total number of participants and percentage with any SAE by preferred term and body system up to three days after SDDR-PEP administration;
- e. the total number of participants and percentage with any drug-related SAE by preferred term and body system up to three days after SDDR-PEP administration;

95% confidence intervals will be calculated for the following statistics:

- a. percentage of participants with any AE, any serious AE, any drug-related AE, any drug-related serious AE;
- b. percentage of participants with the most common AEs, drug-related AEs, SAEs, drug-related SAEs (most common: with an incidence of 10% or more).

These confidence intervals will be calculated based on a random effects logistic regression model with 'island', 'block' (as described above, eight on Anjouan, four on Mohéli, four to six on Madagascar) and 'village' as nested random effects.

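### The 10% cut-off for term-level confidence intervals also covers serious adverse events, so the planned intervals for individual serious terms will be empty

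*SAP*

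**What the plan says.** All of the relevant text is in SAP section 9.2.1, with the safety population defined in 9.1 as everyone who actually received the dose.

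The section first lists descriptive summaries. Summary d is "the total number of participants and percentage with any SAE by preferred term and body system up to three days after SDDR-PEP administration", and summary e is "the total number of participants and percentage with any drug-related SAE by preferred term and body system up to three days after SDDR-PEP administration". Neither has a frequency threshold and neither carries an interval.

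It then states that "95% confidence intervals will be calculated for the following statistics", in two items:

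- Item (a), pooled categories with no threshold: "percentage of participants with any AE, any serious AE, any drug-related AE, any drug-related serious AE".
- Item (b), individual terms: the "percentage of participants with the most common AEs, drug-related AEs, SAEs, drug-related SAEs (most common: with an incidence of 10% or more").

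The threshold in item (b) is defined once, at the end of a list of four categories, and no separate threshold for serious events appears elsewhere in the SAP. All intervals, pooled and term-level, are to come from a random effects logistic model with island, block and village nested.

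The unit of analysis and the observation window are also fixed there: "All AEs will be analyzed based on counts of participants with a specific category and not on counts of individual adverse events", and "Only adverse events that occur between the administration of the drug and three days after administration will be recorded for study purposes".

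**The concern.** A 10% cut-off is a usual way to shorten a table of common, mild events. Serious events are different: few terms are expected, each is rare, and the interest lies in how rare. A threshold of one participant in ten removes all of them.

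Item (b) names serious and drug-related serious events as categories that should receive term-level intervals, so the authors evidently wanted them. The definition attached to the same sentence then prevents them from being produced. At stake is whether the safety report of a preventive treatment, given to people without signs of active leprosy or active pulmonary tuberculosis (exclusion criteria, Table 1 in section 5.1.2), states the uncertainty around each serious reaction seen or only its count and percentage.

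**Working it through.** The SAP gives no expected rate of serious events and no number dosed, so there is no figure to reproduce. The check asks how many affected participants item (b) requires, how likely that is, and what an interval without the cut-off would show.

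**Inputs from the SAP.** Cut-off 10% (9.2.1, item b); confidence level 95% (9.2.1); single dose (2.1); recording for three days (9.2.1); counts of participants (9.2.1); denominator all those dosed (9.1).

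**Assumptions.** Number dosed N from 500 to 40,000. True rate p of one serious term from 0.01% to 10%.

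**Step 1. Affected participants needed for an interval, N / 10.**

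| N dosed | needed for one term |
|---|---|
| 500 | 50 |
| 5,000 | 500 |
| 20,000 | 2,000 |
| 40,000 | 4,000 |

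At N = 20,000, a serious term in 1,999 participants (1,999 / 20,000 = 9.995%) would get no interval.

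**Step 2. Chance of reaching the cut-off.** With X ~ Binomial(N, p), P(X ≥ N/10):

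| true rate p | N = 500 | N = 1,000 | N = 5,000 |
|---|---|---|---|
| 1% | 2.8 × 10⁻³³ | 8 × 10⁻⁶⁵ | effectively 0 |
| 5% | 3.6 × 10⁻⁶ | 8 × 10⁻¹¹ | 5 × 10⁻⁴⁷ |
| 10% | 0.52 | 0.52 | 0.51 |

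Only a serious term with a true rate close to 10% would often qualify.

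**Step 3. Allowing for village clustering.** Blocks hold four villages, one per arm. With 8 blocks on Anjouan, 4 on Mohéli and 4 on Madagascar (the lower of the SAP's four to six), the three PEP arms have (8 + 4 + 4) × 3 = 48 villages. Beta-binomial simulation with assumed intracluster correlations of 0.01 and 0.05, true rates of 0.1%, 1% and 5%, and N = 5,000 and 20,000 gave 0 of 20,000 runs at or above 10% in every setting.

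**Step 4. What an interval without the cut-off would show.** Clopper-Pearson limits for x affected of N are the 0.025 quantile of Beta(x, N − x + 1) and the 0.975 quantile of Beta(x + 1, N − x). They ignore clustering. Per 10,000 dosed:

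| affected | N = 5,000 | N = 20,000 | N = 40,000 |
|---|---|---|---|
| 1 | 0.05 to 11.1 | 0.013 to 2.8 | 0.006 to 1.4 |
| 5 | 3.2 to 23.3 | 0.8 to 5.8 | 0.4 to 2.9 |

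The cut-off, on the same scale, is 1,000 per 10,000.

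**Step 5. What the pooled interval already gives.** Everyone with a given serious term is among those with any serious event, so the pooled upper limit is a ceiling for each term. Suppose N = 20,000, five participants have any serious event and one of them has a particular term. The pooled upper limit is 5.8 per 10,000, and the term's own upper limit is 2.8. The ceiling is valid but about twice as high in this example (5.8 / 2.8 = 2.1).

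**Step 6. Zero events.** The upper limit is 1 − 0.025^(1/N): 7.4 per 10,000 at N = 5,000, 1.8 at 20,000 and 0.9 at 40,000. This case belongs to item (a), for a study with no serious event at all. A rule that covers observed terms would not produce it. The planned logistic model has no finite estimate here.

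**The case against.** The best defence is that nothing rare is hidden. Summaries d and e show number and percentage for every serious term, the denominator is defined, and item (a) gives two serious-event intervals with no threshold. Any reader can compute a simple exact interval from the table. All of this stands, and it makes the point a weakness of reporting. It does not make item (b) work as written. A reader with a table of counts also cannot reproduce an interval that respects the village structure, which the SAP itself chose to model.

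A second defence is that a cut-off keeps modelled intervals to terms that can be estimated. This stands too: with a handful of events spread over many villages, the nested random effects logistic model is unlikely to be stable. Removing the cut-off without changing the method would prescribe intervals that may not be obtainable, so the remedy needs a sparse-data method.

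Three stronger readings are tempting, and the SAP does not support them:

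- A reader might infer that the trial will give no bound at all on a specific serious reaction. The pooled upper limits in item (a) are such bounds, though indirect.
- A reader might take "On a total population screened of just over 102,000 during the first year" (section 3) as the scale of exposure. It counts people screened. Arm 1 receives no PEP, and arms 2 to 4 treat only eligible contacts or, under stated conditions, whole villages. The number dosed remains unknown.
- A reader might argue that a serious term near 10% would halt the programme. The SAP contains no safety stopping rule, and the point does not need one.

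Where the cut-off should lie for non-serious events is a matter of preference, and no change is asked for there.

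**Conclusion.** The point holds in a limited form. The serious and drug-related serious entries of interval item (b) are a planned analysis that will have no output. This follows for every assumed number dosed from 500 to 40,000 and for true rates per serious term up to 5%, well above what is plausible within three days of one dose. It rests on two assumptions that the SAP cannot settle, the number dosed and the rate of serious events, but the conclusion is insensitive to both within these ranges.

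The consequence is small. No data are lost, the efficacy analysis is untouched, and no safety conclusion is reversed. What is missing is a planned measure of uncertainty for each serious term. The correction is desirable and nearly free; it is not a condition for the trial's validity.

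**What to change.** In section 9.2.1, interval item (b), limit the 10% cut-off to adverse events and drug-related adverse events that are not serious. Add that a 95% confidence interval will be given for every serious and every drug-related serious preferred term observed.

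In the sentence on the interval method, add a fallback: where events are too few for the nested random effects logistic model to give a stable estimate, use an exact (Clopper-Pearson) or cluster-adjusted exact interval, and state in the table which was used. Apply the same fallback to item (a) when events are zero or very few. The criterion for switching, such as non-convergence or a minimum number of affected participants, should be written down before the data are analysed.

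The cost is two or three sentences in the SAP and a few more table rows, with no new data. There are two drawbacks: the extra intervals are descriptive only, and simple exact limits ignore village clustering and may be somewhat too narrow, which a table footnote should say.

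### The adverse-event intervals are tied to a random effects logistic model whose usual output is not the participant percentage being reported, and there is no rule for zero events

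*SAP*

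**What the plan says.** SAP section 9.1 defines the safety population: "all participants who effectively received a SDDR-PEP dose are included in the safety analysis". Section 9.2.1 makes the participant the unit: "All AEs will be analyzed based on counts of participants with a specific category and not on counts of individual adverse events". It then asks for 95% confidence intervals for two lists.

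- List (a) is the "percentage of participants with any AE, any serious AE, any drug-related AE, any drug-related serious AE". It has no frequency threshold.
- List (b) covers the commonest individual events in the same four categories ("most common: with an incidence of 10% or more").

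One method is named for both: "These confidence intervals will be calculated based on a random effects logistic regression model", with island, block ("eight on Anjouan, four on Mohéli, four to six on Madagascar") "and 'village' as nested random effects". No fixed covariate is mentioned. The section does not say whether the percentage is read off with the random effects at zero or averaged over them. It gives no alternative for zero events, very few events or a model that does not converge.

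**The concern.** The quantity to be reported is a simple proportion: participants with the event divided by participants dosed. A mixed logistic model without covariates estimates an intercept, which is the log-odds in a village whose island, block and village effects are all zero. Because the logistic curve is not linear, the back-transformed intercept is not the average risk over participants. Below 50% it is smaller, and the gap grows with the spread between villages. An interval built on it is centred too low for the percentage it accompanies.

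Two further problems follow from the same choice. List (a) includes serious and drug-related serious events recorded within three days of dosing, where a count of zero is plausible. The upper limit is then the main safety statement, and the model does not supply one by the standard route. Island also enters as a random effect with three levels, too few to estimate a variance well.

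**Working it through.** The SAP gives no event rate, variance component, number dosed or example interval, so there is no planned figure to reproduce. The inputs are as follows.

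- **Treated villages.** From section 9.2.1, blocks number 8 + 4 + (4 to 6) = 16 to 18. Section 2.1 describes blocks of four ("Within each block villages were randomly and mutually exclusively allocated to the four study arms"). Three arms offer prophylaxis, giving 3 × 16 = 48 to 3 × 18 = 54 treated villages if Madagascar is blocked the same way. The midpoint, 51, is used.
- **Assumed, not in the SAP.** Overall event percentages of 5% and 10%; random-effect SD *s* of 0.5, 1 and 1.5 on the logit scale; 300 dosed per village in simulations; 1,000 to 30,000 dosed in total for the exact limits.

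**Step 1: typical village against participants.** The overall percentage is p = E[expit(b0 + s·Z)], with Z standard normal. Solving for b0 gives the typical-village percentage expit(b0):

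| Overall | s = 0.5 | s = 1 | s = 1.5 |
|---|---|---|---|
| 5% | 4.50% | 3.32% | 2.09% |
| 10% | 9.15% | 7.15% | 4.96% |

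**Step 2: the interval.** The Wald interval is expit(b0 ± 1.96·SE). Counting only the variance-component part, SE = s/√51 if all variation is between villages, and s/√3 if all is between islands.

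- 5%, s = 1, villages: SE = 1/√51 = 0.140, interval 2.54–4.32%. It excludes 5%.
- 5%, s = 0.5, villages: SE = 0.070, interval 3.94–5.13%. It contains 5%.
- 5%, s = 1, islands: SE = 1/√3 = 0.577, interval 1.10–9.62%. It contains 5%.
- 10%, s = 1, villages: 5.53–9.20%. It excludes 10%.

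**Step 3: simulation with fitted models.** With a single village-level random intercept (100 runs per setting), the interval missed the observed percentage in 100% of runs at 5% and s = 1, in 98% at 10% and s = 1, and in none at s = 0.5. That model is simpler than the one planned. When an island term was also fitted (150 runs, true 5%), misses at village SD 1 were about 87%, 61% and 31% for island SDs of 0, 0.5 and 1. At village SD 0.5 they were 0–1% throughout. Coverage of the true percentage stayed below 95% in these island-and-village simulations (15–75%). No simulation included block.

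**Step 4: zero events.** With 51 villages of 300, no events and SD 0.5, the minus log-likelihood is 92.8 at intercept −5, 0.785 at −10, 0.0053 at −15 and 0.00004 at −20. It keeps falling towards 0, so there is no finite maximum, no standard error and no Wald interval. The exact upper limit, 1 − 0.025^(1/N), is 0.368% for 0/1,000, 0.074% for 0/5,000, 0.025% for 0/15,000 and 0.012% for 0/30,000.

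**Step 5: three islands.** If island variance dominates, the interval is in effect a mean of three values with z = 1.96. Its coverage is c/√(2 + c²), the two-sided probability for a t variable on 2 degrees of freedom. With the unbiased variance, c = 1.96 gives 1.96/√5.84 = 0.811. With the maximum-likelihood variance, c = 1.96·√(2/3) = 1.600 gives 1.600/√4.56 = 0.749.

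**The case against.** The strongest reply is that the SAP never says the intercept is back-transformed. It ties the interval to the model and leaves the last step open. Predictions averaged over the random effects come from the same model and do target the participant percentage. This stands: the plan is under-specified on this step, and a reader cannot conclude that it has adopted the typical village as its target.

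A reader might also infer that the safety table will print an interval lying wholly below the observed percentage. The documents do not support that. The miss rates near 100% come from a model with one village-level random effect. The planned island term widens the interval, and the miss largely disappears at a village SD of 0.5 or when variation lies mainly between islands. The SAP gives none of these variances. Equal numbers dosed per village are also a simplification, because arm 2 doses household contacts only, while arm 3 doses everyone eligible within 100 metres.

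A third inference, that the plan understates risk, goes too far. Section 9.2.1 describes deaths and reports counts and raw percentages for all four event categories by preferred term. Only the intervals are in question, and no decision is attached to them.

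The zero-event gap is narrow: it concerns the rare lines of list (a), since an event in list (b) has an incidence of at least 10%. A profile-likelihood or prior-based limit could be found, but the SAP names neither.

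**Conclusion.** The point holds in a limited form. The plan wants an interval for a participant percentage and names a model whose standard output is a different and lower quantity, without the step that would reconcile them. The size depends on variance the SAP does not give. At an overall 5% with village SD 1 and no island variance, the interval is about 2.5–4.3% and excludes the true value. With village SD 0.5, or variation mainly between islands, it would usually contain the observed percentage, although its coverage of the true one can still fall short.

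The lack of a finite estimate with zero events follows from the likelihood and needs no assumption about variance. The three-level island term is a further weakness: where it dominates, a nominal 95% interval covers about 75–81%. This is worth correcting before analysis, but it does not touch the primary result or the raw safety counts.

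**What to change.** Amend section 9.2.1 in one of two ways.

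1. Calculate each interval around the observed participant percentage, on the logit scale, with variance clustered on village and an independence working correlation. An exchangeable correlation need not centre on the observed percentage when village sizes differ.
2. Keep the mixed model, but state that the percentage and its interval come from predictions averaged over the random effects. This corrects the target but leaves the three-level island variance in place.

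The first is simpler and needs no island variance. Adding island as a fixed stratum would not by itself give one overall percentage; that would require standardisation.

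Under either option, use exact (Clopper-Pearson) limits when events are zero or too few to fit, and say in advance what counts as too few. The cluster-robust interval also fails at zero events, so this rule is needed in both cases. List (b) and its 10% threshold can stay, because list (a) already covers any serious and any drug-related serious event.

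The cost is a few sentences and simple code; randomisation and data collection are unaffected. The one drawback is that exact limits ignore clustering, a small matter at very low counts.
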